7.5.1. Functional Assessment of Chronic Illness Therapy (FACIT)-Fatigue Scale

The questionnaires will be analyzed according to the recommendations of the questionnaire authors (see http://www.ser.es/wp-content/uploads/2015/03/FACIT-F_INDICE.pdf). Details of the questionnaire and its algorithm for deriving the score are provided in [Appendix A](#). The questionnaires are considered complete, and the subscale total score can be calculated, if at least 7 of the 13 items were answered by the subject. For each time point, the number and percentage of subjects who complete the questionnaires will be summarized.

The change from baseline in FACIT-F score will be summarized by visit for the FAS.

7.5.2. EQ-5D-5L

The questionnaire will be analyzed according to the recommendations of the authors (see www.euroqol.org). EQ-5D consists of 2 pages – a 5 dimension descriptive system and the EQ visual analogue scale. A copy of the questionnaire is provided in [Appendix B](#).

The descriptive system contains 5 categories: mobility, self-care, usual activities, pain/discomfort and anxiety/depression. The number and percentage of subjects in each response category were tabulated for the FAS. Percentages are based on the number of subjects for whom an assessment is provided at the respective visit.

The EQ visual analogue scale is a visual scale from 0–100 to record a respondent's overall self-rated health state. The respondent is asked to mark an "X" on the scale then record the corresponding number; 0 refers to the worst possible health state, 100 refers to the best possible health state. This will also be presented alongside the 5 dimension descriptive system scores.

The EQ visual analogue scale will be summarized for the observed response and change from baseline for the FAS.

EQ-5D Index Score

The EQ-5D-5L descriptive system can be converted into a single index value, the EQ-5D index score, by using the "EQ-5D-5L Crosswalk Index Value Calculator" provided by the authors (documents and calculation tools will be downloaded from the EuroQol website). The index scores, derived as country specific, are a major feature of the EQ-5D instrument, facilitating the calculation of quality-adjusted life years (QALYs) that are used to inform economic evaluations of health care interventions.

The derived EQ-5D index scores and change from baseline will be summarized by visit for the FAS.

7.5.3. 12-Item Short Form Survey (SF-12)

The questionnaire will be analyzed according to the recommendations of the authors (see <http://campaign.optum.com/optum-outcomes/what-we-do/health-surveys/sf-12v2-health-survey.html>). The SF-12 v2 is a 12-item measure, derived from the original 36-item SF-36, which includes eight (8) health domains which are used to generate a physical component score as well as a mental component score. Each score ranges from 0–100 on a normative scale and may be used to derive a health utility index (SF-6D). A copy of the questionnaire is provided in [Appendix C](#).

The derived scores and change from baseline for the 8 health domains, the physical component score, and the mental component score, will be summarized by visit for the FAS.

7.5.4. Patient Global Impression of Change (PGIC)

The questionnaire (listed in [Appendix D](#)) will be summarized as an ordinal variable by visit for the FAS.

7.5.5. Patient’s Global Impression of [Fatigue] Severity

The change from baseline in questionnaire (listed in [Appendix E](#)) will be summarized as an ordinal variable by visit for the FAS.

7.5.6. Healthcare Resource Utilization

The number of healthcare visits by type (office visit, hospital ER visit, hospitalization, and ICU stay) will be collected and presented in a listing.

8. SAFETY ANALYSIS

Safety data will be summarized for subjects in Safety Analysis Set defined in [Section 4.3](#). The summary tables may also be presented by subgroup based on the baseline weight strata (i.e., BIVV009 dose cohorts). However, the limited number of subjects in each dose cohort and non-randomized assignment preclude a direct comparison between the two dose cohorts.

8.1. Adverse Events

AEs will be classified using the MedDRA system organ classes and preferred terms. MedDRA version 20.1 or higher will be used throughout the study.

In general, AEs will be analyzed based on *incidence*, defined as the proportion of subjects who had at least one occurrence of an event out of the number of subjects in the Safety Analysis Set. An adverse event listing will be provided that will include all adverse events reported with the onset and resolution study days relative to Day 0 (Study Day 1).

All summary table analyses will only include treatment-emergent adverse events unless noted otherwise. The algorithm for the determination of treatment emergence when an onset date is partially or completely missing is described below.

- If the onset time of an adverse event (if time is collected) is missing and the date of onset is the date of dosing, the AE is considered to be a TEAE.
- If the onset day of an adverse event is missing and the month and year of the onset of the AE are either the same or later than the month and year of the first treatment, the AE will be considered a TEAE. If the month and year of the onset of the AE precede the month and year of the first treatment, the AE will not be considered a TEAE.
- If the onset month of an adverse event is missing and the year of the onset of the AE is either the same as or later than the year of first treatment, then the AE will be considered a TEAE. If the year of AE onset precedes the year of first treatment, the AE will not be considered a TEAE.
- If the onset day, month, and year of an adverse event are missing, the AE will be considered to be a TEAE.
- If start date is partial but the stop date can be determined to be before the start of the first dose of study drug, then the AE will not be considered a TEAE.

Unless specified otherwise, system organ classes and preferred terms within each SOC will be presented alphabetically. For the purpose of summarization, a subject is counted once in a SOC or preferred term if the subject reported one or more events in that SOC or preferred term. Unless specified otherwise, percentages will be based on the number of subjects in the Safety Analysis Set.

8.1.1. Overall Summary of Adverse Events

An overall summary of TEAEs will be provided which tabulates the number and percentage of subjects who experienced a TEAE, related TEAE, treatment-emergent SAE, treatment-emergent

related SAE, treatment-emergent Grade 3 or higher AE, or TEAE infections of Grade 3 or higher severity; the number and percentage of subjects who had a TEAE within 24 hours of the start of infusion; the number and percentage of subjects who discontinued treatment and/or the study due to an AE; and the number and percentage of subjects who died.

8.1.2. Treatment-emergent Adverse Events

The incidence of TEAEs will be summarized by SOC and preferred term.

8.1.2.1. Adverse Events in Descending Order of Incidence

A table will be provided which displays TEAE preferred terms in descending order of incidence. Only preferred terms will be included in this table (i.e., the display will not include SOCs).

A similar table will be provided for Grade 3 or higher TEAEs. AEs for which the assessment of severity is missing will be included in this table in the TEAE grade 3 or higher category.

8.1.2.2. Severity of Adverse Events

AEs are classified by the Investigator for CTCAE grades v4.03. A summary of TEAEs by system organ class, preferred term, and CTCAE grade will be presented. AEs with a missing severity will be excluded from this table and listed separately to supplement the summary table. A subject will be counted once for each SOC and preferred term based on the greatest severity within that SOC and preferred term, respectively.

8.1.2.3. Relationship of Adverse Events to Study Drug

AEs are classified by the Investigator for relationship to study drug (“Unrelated,” “Possible,” and “Probable”). For summary tables, an AE with relationship of “Possible” or “Probable” will be considered “Related.” A summary of TEAEs by SOC, preferred term, and relationship (“Related” or “Unrelated”) will be presented. AEs with a missing relationship will be counted as “Related” in the summary table. A subject will be counted once for each SOC and preferred term based on the highest relationship within that SOC and preferred term, respectively.

8.1.3. Serious Adverse Events

Any AE reported as resulting in death, immediate risk of death (life threatening), inpatient hospitalization or prolongation of existing hospitalization, persistent or significant disability/incapacity, or a congenital/anomaly/birth defect will be classified as an SAE by the Investigator. An SAE may also be any other medically important event that, in the opinion of the Investigator, may jeopardize the subject or may require intervention to prevent one of the other outcomes listed above. In addition, if a subject develops a Grade 3 or higher allergic reaction per Common Terminology Criteria for Adverse Events (CTCAE) grading or an anaphylactic reaction in association with BIVV009 administration, the event should be reported as an SAE per protocol.

All SAEs will be listed; treatment-emergent SAEs and treatment-emergent related SAEs will be summarized by system organ class and preferred term.

8.1.4. Adverse Events Leading to Treatment Discontinuation and/or Study Withdrawal

AEs leading to treatment discontinuation and/or study withdrawal will be listed. All AEs reported on the AE log for the item “Action Taken with Study Drug” with a response of “Study drug permanently discontinued” or for the item “Was the subject terminated from this study due to this AE?” with a response of “Yes” will be included.

8.1.5. Deaths on Study

A listing of deaths occurring on study will be provided.

8.1.6. Adverse Events of Interest

8.1.6.1. AEs Within 24 Hours after the Start of Infusion

All AEs within 24 hours after the start of infusion are captured in the eCRF. Incidence of AEs within 24 hours after the start of infusion will be summarized by SOC and preferred term.

8.1.6.2. Infections and Infections of \geq Grade 3 Severity

Infections will be captured based on MedDRA SOC of “infections and infestations.” Incidence of infections of Grade 3 or higher will be summarized by preferred term. A listing of all infections, infections of Grade 3 or higher and serious infections will be provided.

8.1.6.3. Haemolytic Breakthrough

Proportion of subjects with hemolytic breakthrough (defined in [Section 5.1.1](#)) at any visit will be summarized. The date (visit) of onset and hemolytic lab parameters (i.e., Hgb, bilirubin, LDH, and haptoglobin) over time will be listed for subjects with haemolytic breakthrough.

8.2. Clinical Laboratory Evaluations

All laboratory data will be provided in data listings; abnormal values relative to laboratory normal ranges will be identified.

8.2.1. Hematology and Chemistry

All summaries will be structured such that the hematology and chemistry tests are presented in the order shown in the tables below.

Hematology measurements that will be summarized and listed include white blood cell count (WBC), red blood cell count (RBC), differentials (basophils, eosinophils, lymphocytes, monocytes, neutrophils, reticulocytes), hemoglobin, hematocrit, and platelet count.

Chemistry measurements that will be summarized and listed include electrolytes (sodium, potassium, chloride), glucose, total protein, total bilirubin, alanine aminotransferase (ALT), aspartate aminotransferase (AST), alkaline phosphatase (ALP), blood urea nitrogen (BUN), and serum creatinine.

8.2.1.1. Change from Baseline

Hematology and chemistry results at baseline and post baseline visits, along with change from baseline, will be summarized with descriptive statistics for Safety Analysis Set.

8.2.1.2. Shifts

Each subject's laboratory values will be classified according to whether the test result is "low" (below the LLN), "normal" (within the normal range), "high" (above the ULN). Shift tables will be constructed based on both the minimum and maximum post-baseline values for each subject. Data collected from unscheduled visits will be included in the determination of the per subject minimum and maximum values. A separate table will be provided which summarizes the results of the shift tables in which the number and percentage of subjects with a shift to low (from normal, high, or unknown) and the number of subjects with a shift to high (from normal, low, or unknown) will be tabulated; percentages will be based on the number of subjects at risk. The number at risk for a shift to low (high) is the number of subjects whose baseline value was not low (high), including unknown, who had at least one post-baseline value. Only directions of change indicating a clinical concern will be included in this table summarizing the shifts. The direction of concern is provided in [Table 8](#).

Table 8: Direction of Change Indicating Clinical Concern for Laboratory Tests

Laboratory Test	Direction	Laboratory Test	Direction
Chemistry		Hematology	
Liver		White blood cells	Low and High
ALT/SGPT	High	Lymphocytes	Low and High
AST/SGOT	High	Neutrophils	Low and High
Total bilirubin	High	Monocytes	Low and High
Indirect bilirubin	High	Eosinophils	Low and High
Renal		Basophils	Low and High
Blood urea nitrogen	High	Red blood cell count	Low and High
Creatinine	High	Hemoglobin	Low and High
Electrolytes		Hematocrit	Low and High
Sodium	Low and High	Platelets	Low and High
Potassium	Low and High		
Chloride	Low and High		
Other			
Glucose	Low and High		
Total protein	Low and High		

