5.1 INCLUSION CRITERIA

All patients must meet all the following inclusion criteria to be enrolled:

1. Adult males and female patients ≥ 18 years of age at Screening.
2. Body weight of ≥ 39 kg at Screening.
3. Confirmed diagnosis of primary CAgD based on the following criteria:
 - a) Chronic hemolysis
 - b) Polyspecific direct antiglobulin test (DAT) positive
 - c) Monospecific DAT strongly positive for C3d
 - d) Cold agglutinin titer ≥ 64 at 4°C
 - e) IgG DAT $\leq 1+$, and
 - f) No overt malignant disease
4. History of at least one documented blood transfusion within 6 months of enrollment.
5. Hemoglobin level ≤ 10.0 g/dL.
6. Bilirubin level above the normal reference range, including patients with Gilbert's Syndrome
7. Ferritin levels above the lower limit of normal. Concurrent treatment with iron supplementation is permitted if the patient has been on a stable dose during the previous 4 weeks.
8. Presence of one or more of the following CAgD-related signs or symptoms within 3 months of Screening:
 - a) Symptomatic anemia defined as:
 - i. Fatigue
 - ii. Weakness
 - iii. Shortness of breath
 - iv. Palpitations, fast heart beat
 - v. Light headedness, and/or
 - vi. Chest pain
 - b) Acrocyanosis

- c) Raynaud's syndrome
 - d) Hemoglobinuria
 - e) Disabling circulatory symptoms, and/or
 - f) Major adverse vascular event (including thrombosis)
9. Bone marrow biopsy within 6 months of Screening with no overt evidence of lymphoproliferative disease or other hematological malignancy. An additional bone marrow biopsy will be required if the prior bone marrow is deemed unsuitable for analysis by the Sponsor.
 10. Documented vaccinations against encapsulated bacterial pathogens (*Neisseria meningitidis*, including serogroup B *meningococcus* where available, *Haemophilus influenzae*, and *Streptococcus pneumoniae*) within 5 years of enrollment or as specified in [Section 6.1.1.1](#).
 11. Adequate IV access.
 12. If female, must be post-menopausal, surgically sterile, or be established on (≥ 3 months prior to Screening) and agree to continue to use the same highly effective methods of birth control throughout the study and for 9 weeks following administration of the last dose of study drug.
 13. Males must be surgically sterile for at least 90 days or when sexually-active with female partners of child-bearing potential will agree to use highly effective contraception from Day 0 until 9 weeks following administration of the last dose of study drug.

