8.2.1.3. Potentially Clinically Significant Laboratory Abnormalities

Abnormal laboratory values (excluding Hgb, reticulocytes, haptoglobin, bilirubin, and LDH) will also be evaluated by determining the number and percentage of subjects with at least one potentially clinically significant laboratory abnormality over the course of the study that also represents a worsening from baseline. The potentially clinically significant levels are based on Grade 2 or higher thresholds from the CTCAE v4.03 where possible, or are defined by Sponsor's safety group. Subjects who have a post baseline laboratory value that meets the criteria for being potentially clinically significant but do not have a baseline value will be included in the numerator for determining the percentage of subjects with an abnormality. Data collected from unscheduled visits will be included in this analysis.

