5.1.1. Definitions

Study Day

Study Day is defined as days relative to the date of first dose of BIVV009 in Part A, Day 0. The start/stop day of events will be calculated as (date of event – date of Day 0 +1).

Incomplete dates will be imputed for the calculation of study days, unless specified otherwise:

- If missing day only, the start date will be imputed as the first day of the month, while the end date will be imputed as the last day of the month;
- If missing day and month, the start date will be imputed as the first day of the year, while the end date will be imputed as the last day of the year;

Baseline

Baseline is defined as the last non-missing value prior to the first administration of study drug in Part A. If a transfusion occurred during the screening period, the baseline measure must be at least 7 days after the transfusion.

Study Treatment Period

For subjects who enroll into Part B, the Part A study treatment period starts at the date of first study drug administration and ends at the date of Week 26 visit. The Part B study treatment period starts following completion of Part A (ie, immediately following Week 26 visit) and ends at the ET/EOS/Safety follow-up visit, which is 9 weeks after each subjects' last dose.

The Combined Study Period includes all visits in Part A and Part B and will be utilized for a subset of analyses in order to support regulatory submissions and/or publications.

Visit Windows

Analysis by study visit will utilize the data recorded on the corresponding nominal visit from electronic Case Report Forms (eCRFs). In case of missing data/assessments for a visit, data from an unscheduled visit, or ET/Safety Follow-up Visit will be used, if the Study Day of such a

visit fits in the analytic window defined below. If multiple values are identified within the analytic window, the one closest to the target study day will be used.

- Starting at Week 27 and every 2 weeks thereafter, analytic visit windows in Part B will be -6 days to +7 days from the Target Study Days of the protocol-defined visits. An example of the first few visits in Part B can be seen in Table 1, below.

Table 1: Analytic Visit Windows

Visit	Target Study Day	Analytic Visit Window (Study Day)
Week 27	189	183-196
Week 29	203	197-210
Week 31	217	211-224
Week 33	231	225-238
Etc.		

Solicited Symptomatic Anemia

Refer to the Part A SAP for definitions regarding the severity of CAD symptomatic anemia.

Thromboembolic Events

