8.2.1.3. Potentially Clinically Significant Laboratory Abnormalities

Abnormal laboratory values (excluding LDH, haptoglobin, and reticulocytes) will also be evaluated by determining the number and percentage of subjects with at least one potentially clinically significant laboratory abnormality over the course of Part B of the study that also represents a worsening from baseline. The potentially clinically significant levels are based on Grade 2 or higher thresholds from the CTCAE v 4.03 where possible, or are defined by Bioverativ’s safety group. Subjects who have a post baseline laboratory value that meets the criteria for being potentially clinically significant but do not have a baseline value will be included in the numerator for determining the percentage of subjects with an abnormality.

All data collected during Part B, including data collected from unscheduled visits, will be included in this analysis.

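### The at-risk laboratory shift summary tells little about total bilirubin (High) and haemoglobin (Low), and for bilirubin no other patient-count safety table fully closes the gap

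*SAP*

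**What the plan says.** **Shift rule.** Part A SAP 8.2.1.2 builds full shift tables on each patient's minimum and maximum post-baseline value. It then adds a summary of shifts to low or high, with percentages over a restricted denominator: "The number at risk for a shift to low (high) is the number of subjects whose baseline value was not low (high), including unknown", provided there is a post-baseline value. In Table 8 the liver block has "Total bilirubin High" and a High row for indirect bilirubin; the haematology block has "Hemoglobin Low and High". Part B SAP 8.2.1.2 uses the same rule. Its Table 2 keeps total bilirubin (High), has no indirect bilirubin, and lists GGT.

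**Baseline.** Part A SAP 5.1.1 takes the last value before study drug. Part B SAP 5.1.1 keeps the same reference: "Baseline is defined as the last non-missing value prior to the first administration of study drug in Part A".

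**Eligibility.** Protocol 5.1 requires "Bilirubin level above the normal reference range, including patients with Gilbert's Syndrome" (criterion 6) and haemoglobin of at most 10.0 g/dL (criterion 5).

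**Abnormality tables.** Part A SAP 8.2.1.3: "Abnormal laboratory values (excluding Hgb, reticulocytes, haptoglobin, bilirubin, and LDH) will also be evaluated". Part B SAP 8.2.1.3 leaves out only LDH, haptoglobin and reticulocytes, but counts patients with "at least one potentially clinically significant laboratory abnormality over the course of Part B of the study that also represents a worsening from baseline".

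**What is collected.** The chemistry panel in Protocol Appendix A contains total, direct and indirect bilirubin and alkaline phosphatase. It does not contain GGT. Direct bilirubin and alkaline phosphatase appear in neither shift table.

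**The concern.** An at-risk shift count is useful when most patients start within range. Here the entry criteria place patients outside it, on the side that the row is meant to detect. A patient who starts high on bilirubin cannot shift to high, however far the value later rises. Nor can one who normalises on treatment and rises again, because the reference stays the untreated value.

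Bilirubin has two roles in this trial. As a haemolysis marker it is an efficacy variable and is expected to fall on treatment. It is also a liver safety test, and both SAPs list it as one. Long-term safety is the primary objective of Part B, and the same rule serves Part A. A nearly empty bilirubin row could be read as reassurance when the denominator has largely settled it in advance.

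**Working it through.** **1. Inputs.** The plan gives no at-risk count to reproduce. The only design figure used is the sample size of about 20 (Protocol 7.10). Eligibility is judged on the first screening laboratory set (Protocol 6.1.1.1), for which local values are allowed (Protocol 6.3.7). Baseline is the last pre-dose value. Screening lasts 6 weeks, extendable by 1 week for a transfusion (Protocol Table 3, footnote a).

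**2. Total bilirubin, shift to high.** Let q be the share of patients no longer high at Day 0. The documents do not give q, so it is varied. The number at risk is m = 20 × q. If a fraction p of those at risk develops a new high value, the chance that the row shows at least one is 1 − (1 − p)^m. The values of p are also assumptions.

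| q (assumed) | m at risk of 20 | p = 10% | p = 20% |
|---|---|---|---|
| 0% | 0 | 0% (row is 0/0) | 0% |
| 5% | 1 | 10% | 20% |
| 10% | 2 | 19% | 36% |
| 20% | 4 | 34% | 59% |
| 30% | 6 | 47% | 74% |

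For example, with m = 4 and p = 10%: 1 − 0.9^4 = 1 − 0.656 = 0.344.

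**3. Haemoglobin.** The lower limit of normal is not in the documents. Take about 12 g/dL as an assumption; the Part A SAP uses that value for normalisation. A patient eligible at 10.0 g/dL or less would need a rise of at least 12 − 10 = 2 g/dL before Day 0 to be at risk for a shift to low. That denominator is about 0. For a shift to high it is up to 20 of 20.

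**4. One patient followed through the outputs.** Suppose bilirubin is 3 × ULN at baseline, in range at Week 26, and 2 × ULN later in Part B from a hepatic cause (illustrative values).

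- At-risk summary: baseline high, so not at risk and not counted.
- Part B 8.2.1.3: 2 is below 3, so not a worsening and not counted.
- Change from baseline: 2 − 3 = −1 × ULN, which still reads as improvement.
- Full shift table on the maximum: Part B uses Part B data only, so the patient moves from high-to-normal to high-to-high. That cell also holds patients who never normalised and those whose haemolysis returned.
- Listings: the value is flagged as abnormal.
- ALT/AST shift rows: counted only if a transaminase that was in range at baseline also goes high.

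If the same rise came in Part A, section 8.2.1.3 would not show it, because bilirubin is excluded. The full shift table would use the maximum from Week 1 onward, so a value still high early on treatment already gives high-to-high. The by-visit proportion with normal bilirubin (Part A SAP 7.4.1.2) would lose one patient. The Part B SAP plans no such proportion.

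**The case against.** The strongest reply is that the blind spot is confined to one derived summary. Full shift tables, by-visit change from baseline, flagged listings and ALT/AST shifts are all planned. ALT, AST and alkaline phosphatase are not excluded from either abnormality table. Laboratory changes with symptoms or a treatment change are reported as adverse events (Protocol 6.7.3). Protocol 7.8.2 takes efficacy parameters out of the laboratory safety summaries, which may explain why Part A 8.2.1.3 drops haemolysis markers. A zero denominator would also be visible in the table. All of this stands, and it limits the point to reporting. It does not supply a patient count for a bilirubin rise on treatment, and the SAPs themselves keep bilirubin among the liver tests.

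For haemoglobin the reply largely succeeds. Hemolytic breakthrough is a fall of at least 2 g/dL from the last scheduled visit with a marker change. It is counted in Part A (8.1.6.3) and over all Part B data (7.2.2), so an on-treatment reference already exists.

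A reader might infer that the rule can never fire for either test. The documents do not support that. Haemoglobin also has a High row, and the SAP says "the number of subjects with a shift to high (from normal, low, or unknown) will be tabulated", so patients low at baseline are at risk there. A reader might also infer that all patients must be high or low at baseline. That is not forced: eligibility rests on the first screening set, local values are allowed, transfusion may intervene up to 7 days before the first dose, and unknown baselines count as at risk. Protocol 6.1.2 re-checks eligibility on Day 0 but states no laboratory re-test. Criterion 6 does not name indirect bilirubin, so an empty row there is likely but not certain.

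**Conclusion.** The point holds in limited form. The at-risk summary is largely uninformative for total bilirubin (High) and haemoglobin (Low) in both parts, with a denominator of zero or a handful of about 20. For bilirubin, no other patient-count safety table fully covers a rise on treatment: Part A excludes the test, and Part B measures worsening from the untreated value. The data are not lost; what is missing is an informative count. Separately, the GGT row in Part B Table 2 has no matching test in Appendix A.

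The detection chances above only illustrate how the row depends on its denominator. They rest on assumed values of q and p and do not estimate hepatic risk. It would be tempting to set them against the chance of detection with all 20 patients at risk, but that is not a fair yardstick. No reference proposed here would put all 20 at risk, because patients who do not normalise stay outside the denominator. Efficacy results, alpha and sample size are unaffected.

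**What to change.** 1. Add direct bilirubin (High) to Part A Table 8 and Part B Table 2, and to the chemistry measurements named in section 8.2.1 of each SAP. Also count patients with ALT or AST and direct bilirubin above ULN at the same draw.
2. For Part B, also compute the total bilirubin shift and the worsening test from the Week 26 value. Take the at-risk denominator from that reference and print it.
3. Replace GGT in Part B Table 2 with alkaline phosphatase, which is collected.

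The cost is SAP wording and a few table rows. The direct bilirubin, transaminase and alkaline phosphatase values are already in the chemistry panel, which is scheduled at Week 26. If the Part A analysis has already been run, its items can be supplementary tables. There are limits: returning haemolysis will also appear in the Week 26-referenced total bilirubin row, which is why direct bilirubin should be shown beside it, and patients who never normalise, including any with Gilbert's syndrome who stay high, remain outside that row's denominator.
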